12.0 Statistical Considerations

If a study incorporates qualitative rather than quantitative methods, indicate this and describe qualitative analysis and disregard the rest of this section: This study does not incorporate qualitative data analysis.

Describe how the data will be examined and statistically analyzed to answer the objectives: Go/no-go accuracy will be evaluated in a 2 x 2 repeated measure ANOVA, with group, treatment and treatment x group interaction entered into the model.

Provide a brief sample size calculation or description of sample size calculation. Include methods and assumptions such as loss to follow-up, as appropriate: Effect size is estimated from Luijten et al (2011). In that study, effect size was 0.24.

We anticipate 120 participants completing the study. An a priori power analysis was conducted using G*power 3.1.9.2 for an ANOVA test, repeated measures and within-between interaction. With 2

within and 2 between factors; a base correlation=0.6; power=0.95; alpha=0.05, the total of 120 participants (60 per group) is required to capture an interaction between group and treatment on ERN.

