7.0 Expected Risks/Benefits

Include expected risks and benefits to subjects and/or society: There are no expected benefits to the participants of this research study, however, it is expected that a better understanding of biomarkers will lead to more sophisticated smoking cessation treatments.

There may be side effects associated with placebo and intranasal insulin administration. One common side effect of placebo is nasal burning and irritation due to a high salt content. Based on the results of our earlier INDs with the same 60 IU dose of intranasal insulin, we don't anticipate any risks of particular severity or seriousness. Nonetheless, as in our previous IND studies, we will complete a detailed evaluation of circulating glucose and olfactory function. Following each of the three rounds of administration, on a scale of 1-10, the following will be assessed: 1. Pain, 2. Burning, 3. Taste, 4. Cough and 5. Anything else participants wish to rate with regards to local irritation.

To ensure that participants' blood glucose levels are not adversely affected by intranasal insulin administration, we will measure blood glucose levels for an immediate glucose level reading to ensure that participants are not hypoglycemic. If a study subject tests below euglycemic level (<70 mg/dL) at any point during the study, the session will be stopped and the subject will be treated. A hypoglycemic subject will be given 15 grams of glucose (4 oz of orange juice) and their glucose level will be rechecked in 15 minutes. The process will be repeated if they are still hypoglycemic. Once treated, they will be given a snack (a granola bar) to eat in order to prevent recurrence. Subjects will then engage in a light activity such as reading for an hour. Following this hour, subjects will drink 4 ounces of orange juice and eat a granola bar. At this time, we will retest their blood glucose levels. Upon confirmation that the subject is still euglycemic, he/she will be discharged.

To assess olfactory function, all subjects will undergo a baseline smell test, and only individuals with normal smell function (identifying 11 or 12 out of 12 total smells) will be eligible to participate in the study. Sniffin' Sticks involves presentation of 12 different pens containing different smells. After the presentation of each pen, participants complete a multiple-choice question with 4 possible choices; one of which is the answer corresponding to the correct smell.

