Describe stopping rules for the study: Stopping rules for the study will apply to expedited cases in which the probability of study treatment causality is high or a case of a change to the risks or potential benefits of the research (such as safety monitoring indicates that a particular side effect is more severe, or more frequent than initially expected). In the case of an expedited event, the study will be stopped until further information is gathered and a potential plan is formulated through consultation with the IRB.

Describe what occurs if a subject withdraws prematurely: The PI and an appointed research team member will provide guidance to participants on the most appropriate method of discontinuation based on where they are in the study protocol. Recommendations will be given based on what procedures the subject has completed. For example, if the participant decides to withdraw participation immediately after receiving a spray, researchers will counsel the participant on common side effects they may experience. Researchers will provide a discharge summary of the session based on what the participant has completed. The team will provide supportive care to subjects as needed following all premature discontinuations.

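### The repeated-measures ANOVA discards participants with only one scored session; a mixed model with the same terms would keep them at almost no cost

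*Combined protocol and SAP*

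**What the plan says.** Section 12.0 (Statistical Considerations) gives one analysis: "Go/no-go accuracy will be evaluated in a 2 x 2 repeated measure ANOVA", "with group, treatment and treatment x group interaction entered into the model". It defines no analysis population, no handling of a missing session, no loss rate and no replacement rule, although the section's own prompt asks about loss to follow-up. The only related statement is "We anticipate 120 participants completing the study".

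Other sections show how a session score can be missing:
- Section 6.0 schedules two sessions at least a week apart.
- Section 6.1 (outline of the study session) repeats urine and breath eligibility tests at the start of each session.
- Section 7.0 says that if glucose falls below 70 mg/dL, "the session will be stopped and the subject will be treated".
- Section 11.0 considers what happens "if the participant decides to withdraw participation immediately after receiving a spray". It covers counselling and discharge, not use of the data.

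**The concern.** In a 2 x 2 design with one within-person factor, the treatment and interaction tests are tests on each person's difference between sessions, and the group test is on each person's mean of the two. A participant with one score has neither, so the ANOVA drops that person. The plan does not say so; it follows from the method named.

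Two things are at stake. Observed session-1 data are thrown away, which costs precision. And completers may differ from everyone randomised. That matters most for the group contrast, because Section 3.0 sets out to evaluate accuracy as a biomarker of smoking behaviour.

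**Working it through.** **Inputs from Section 12.0.** 60 per group; "a base correlation=0.6; power=0.95; alpha=0.05"; "In that study, effect size was 0.24". No loss rate is given, so 5-20% is assumed. The calculations include no session effect, because the planned model has none.

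**The plan's own figure.** Section 12.0 states that "the total of 120 participants (60 per group) is required to capture an interaction between group and treatment on ERN". For the within-between interaction, λ = f²·N·m/(1-ρ), with m = 2, ρ = 0.6 and degrees of freedom 1 and N-2.
- Reading 0.24 as f: λ at N = 120 is 0.0576 × 120 × 2 / 0.4 = 34.56. Power exceeds 0.999, and 48 participants would give 0.95.
- Reading it as d (f = 0.12): λ = 0.0144 × 120 × 2 / 0.4 = 8.64. Power is 0.83, and 184 would be needed.
- N = 120 at power 0.95 corresponds to f of about 0.148.

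So 120 does not follow from the stated inputs. That is a separate matter, and nothing below depends on it.

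**Complete data.** In one simulated trial (60 per group, ρ = 0.6) the interaction estimate was 0.3811 in both models. F was 5.998 from the ANOVA, and the squared Wald statistic was 5.998 from the REML random-intercept model. This equality needs a non-negative within-person covariance. In a simulated data set with negative correlation the statistics differed (0.036 v 0.056), but the plan assumes +0.6.

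**Precision for treatment and interaction.** Let a share d have one session, half on each treatment. Per group of n, in units of the score variance:
- completers: variance = 2(1-ρ) / [(1-d)n]
- all available data: variance = 2 / [(1-d)n/(1-ρ) + dn/2]
- ratio = (1-d) / [1 - d(1+ρ)/2] = (1-d)/(1-0.8d)

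| d | Variance ratio | Effective N, ANOVA: 120(1-d) | Effective N, mixed model: 120(1-0.8d) |
|---|---|---|---|
| 5% | 0.95/0.96 = 0.990 | 114 | 115.2 |
| 10% | 0.90/0.92 = 0.978 | 108 | 110.4 |
| 15% | 0.85/0.88 = 0.966 | 102 | 105.6 |
| 20% | 0.80/0.84 = 0.952 | 96 | 100.8 |

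The mixed model recovers (1-ρ)/2 = 20% of the lost information. If f were 0.15, power at 120 would be 0.954; at 15% loss it falls to 0.918 with the ANOVA and about 0.926 with the mixed model.

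**Bias in the interaction.** In 300 simulated trials with a true value of 0.30 and 15% missing session 2, the means were 0.307 (ANOVA) and 0.310 (mixed model) under random loss, and 0.284 and 0.290 when loss depended on the session-1 score. Simulation error is about 0.01, so neither method stands out.

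**Bias in the group contrast.** Assume the odds of missing session 2 are multiplied by e for each SD lower session-1 score. Let b(p) be the mean standardised session-1 score among completers when a share p is lost. At session 2 the shift is ρb, so averaged over sessions it is (1+ρ)/2 × b = 0.8b. Numerical integration over a normal score gives:

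| Loss p | b(p), session 1 | 0.8·b(p), both sessions |
|---|---|---|
| 5% | 0.047 | 0.04 |
| 6% | 0.056 | 0.045 |
| 10% | 0.091 | 0.073 |
| 15% | 0.133 | 0.106 |
| 20% | 0.173 | 0.14 |

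With an assumed true smoker deficit of 0.50 SD, completers would show:
- 15% of smokers and 6% of non-smokers lost: 0.50 - (0.106 - 0.045) = 0.44, or 12% too small
- 10% and 6%: 0.50 - (0.073 - 0.045) = 0.47
- equal loss: 0.50

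Simulation agrees. At 15% v 6%, 3,000 trials gave 0.441 for completers and 0.502 using all available data. At 10% in both groups, 600 trials gave 0.511 and 0.507.

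**The case against.** The strongest reply is that little changes where the trial is powered. The sample size is for the interaction, and there the gain at 15% loss is 3.6 effective participants out of 120, with no visible difference in bias. The planned 120 is already a count of completers. All of this stands, and it makes the point an inexpensive improvement rather than a flaw that threatens the result.

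A reader might also infer more than the documents support:
- **That the smoker deficit will be understated.** This needs loss that differs by group and also tracks session-1 accuracy. The plan asks smokers to refrain from smoking until each session ends, so unequal loss is conceivable, but the documents give no loss rates and no link to accuracy.
- **That a mixed model rescues everyone who is stopped or withdraws.** A person who leaves straight after the first spray has no task score under any model. The session outline places glucose checks before the spray and at discharge, after the task. A low reading at the first check means that session has no score under either model; a low reading at discharge leaves a scored session. Sections 2.0 and 7.0 also report no hypoglycaemia in the earlier studies.
- **That the mixed model always rests on a weaker assumption.** It relies on data missing at random. When loss was simulated only after insulin-first, driven by a stable personal level (30% and 12% in that sequence, true treatment effect 0), the mixed model was biased by -0.020 (SE 0.003) and completers gave 0.004. When loss instead depended on the observed score, completers gave 0.031 and the mixed model 0.001. Neither method wins under every mechanism, and the biases are small.

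**Conclusion.** The point holds as a cheap improvement. The only planned analysis discards participants with one scored session, and the plan does not say how they are to be handled. At ρ = 0.6, keeping them reduces the variance of treatment and interaction effects by about 1-5% when 5-20% have one session, with no material change in bias if loss depends on the session-1 score.

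The group contrast among completers is attenuated only under loss that is both unequal and score-dependent: about 0.44 SD instead of 0.50 at 15% v 6%, about 0.47 at 10% v 6%, and no bias at equal loss. The loss rates, the selection strength and the 0.5 SD deficit are assumptions; only the correlation and the group sizes come from the plan.

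**What to change.** In Section 12.0, make the primary analysis a linear mixed model for go/no-go accuracy with group, treatment and their interaction as fixed effects, a participant random intercept, REML estimation and Kenward-Roger degrees of freedom. Include every randomised participant with at least one scored session. Define a scored session, and report by group and sequence how many participants have two, one or no scores. Keep the complete-pairs ANOVA as a sensitivity analysis, because it can be slightly less biased for the treatment effect if loss follows an unobserved stable personal level.

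The cost is a few sentences and one model call. With complete data and a non-negative within-person covariance, the interaction test is the planned one. The downside is reliance on missing at random, which should be stated.

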1.0 Project Summary/Abstract

This program of research focuses on identifying neurologic biomarkers of smoking behavior in order to develop individualized smoking cessation aids. The research team has carefully designed the study protocol to ensure participant safety and confidentiality. This research will include administration of intranasal insulin and a placebo comparator. The intranasal insulin administered is an investigational drug and has been granted IND status by the FDA (IND#129432). During the times of drug effects, we will evaluate a biomarker using non-invasive equipment. Researchers are trained to be vigilant in identifying any side effects associated with the study drug and associated procedures. Anticipated risks of study drugs and equipment have been recognized by the research team and will be discussed as part of the informed consent process. Access to data collection and sensitive patient information will be limited to the Principal Investigator and designated research team. Researchers have quality control metrics in place to assure collection of accurate data, proper documentation of study activities, and predeveloped contingency plans in the event unanticipated problems occur.

Schemas are welcomed and often provide a nice visual reference for the project: The proposed work is a 2-session crossover design study intended to evaluate the effects of intranasal insulin vs placebo in smokers and non-smokers. Study participants will be randomized to either receive Treatment A (intranasal insulin) or Treatment B (placebo) during each session (Figure 1). The washout period will be 1 week in duration. Study participants will consist of healthy smokers and healthy non-smokers. Period 1 represents the first testing session and Period 2 represents the second testing session. As discussed in the above-section, one specific treatment will be administered per session.

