3.0 Objectives/Aims

Identify hypotheses being tested/primary endpoints/primary purpose of the protocol: The aim of the proposed work is to evaluate go/no-go accuracy as a neurologic biomarker of smoking behavior. Our hypothesis is that following intranasal insulin administration, smokers will have an improved go/no-go accuracy.

Study duration: This duration of the research study is 2 years starting January 2018 – January 2020.

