6.0 Study Design and Procedures

List any collaborating sites where human subjects research will be performed, and describe the role of those sites and collaborating investigators in performing the proposed research (if applicable): This study will be only conducted at University of Illinois. Study space will be rented at Center for Clinical and Translational Science. In addition, UIC nurse will be responsible for performing nasal examination and collecting blood samples. Study personnel – working out of the PI's laboratory - will ensure regulatory compliance, recruit participants, as well as collect and analyze the data. The PI's lab is located on the first floor of UIC College of Pharmacy. Study materials, equipment and all paper copies will be locked in the office of research staff affiliated with the study.

Describe the study design. The description should be capable of meeting the study objectives: This is a two group, two session study. The only eligibility criteria separating the two groups is the smoking status, otherwise the study population will consist of healthy volunteers. Following successful completion of the "Initial Survey", study participants will be scheduled for a 3-hr In-Person Screening visit. At the in-person screening, participants will 1. be consented, 2. provide urine and breath samples, 3. complete surveys, and 4. receive study instructions. After the completion of the "In-Person Screening", study participants will be scheduled for two study sessions, separated by a minimum of 1 week. During the study session, in random order, study participants will receive either intranasal insulin (60 IU) or placebo. This is a cross-over study –participants receiving intranasal insulin will receive placebo next, and vice-versa. Please refer to Table 1 for a summary of the study

session. The sessions will be identical, other than participants receiving intranasal insulin or placebo in random order.

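### The two-session crossover ANOVA has no period term, so a change between sessions mainly costs precision that one added term would keep

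*Combined protocol and SAP*

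**What the plan says.** Section 1.0 describes a two-session crossover and labels the sessions: "Period 1 represents the first testing session and Period 2 represents the second testing session". Section 6.0 says that "in random order, study participants will receive either intranasal insulin (60 IU) or placebo", and that "participants receiving intranasal insulin will receive placebo next, and vice-versa". The two sessions are otherwise meant to be the same: "The sessions will be identical, other than participants receiving intranasal insulin or placebo in random order".

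The hypothesis in Section 3.0 concerns smokers: "Our hypothesis is that following intranasal insulin administration, smokers will have an improved go/no-go accuracy". The analysis text in Section 12.0 is one sentence. It says "Go/no-go accuracy will be evaluated in a 2 x 2 repeated measure ANOVA", "with group, treatment and treatment x group interaction entered into the model". The sample size is set for the interaction: "the total of 120 participants (60 per group) is required to capture an interaction between group and treatment on ERN".

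No available section adds period, session or order to the model. The available text also does not say whether order is balanced within smoking group. Figure 1 is not shown, and the section numbering runs from 8.0 to 11.0, so Sections 9.0 and 10.0 could not be consulted.

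**The concern.** A session effect is plausible. The outcome is performance on a computerised task of 490 trials (412 + 78, Section 6.1). The screening steps listed in Section 6.0 include no practice run, so on the text available participants first meet the task in session 1 and repeat it in session 2.

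Such a change has two consequences if period is not modelled. First, it adds to the variance of the insulin-placebo differences, because it enters with opposite signs in the two orders. Second, if the orders are unevenly represented, part of it moves into the estimate. The insulin effect in smokers shifts if order is uneven among smokers. The group-by-treatment interaction shifts only if the split differs between smokers and non-smokers. What is at stake is mainly power for the interaction.

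**Working it through.** **Inputs.** From Section 12.0: 60 per group, correlation 0.6, alpha 0.05, power 0.95, effect size 0.24 with no metric named. These were given for ERN, while the planned analysis is of accuracy, so applying them to accuracy is an assumption. The session effect is not in the documents. I assume 0.1, 0.25 and 0.5 SD of the paired difference. At correlation 0.6 the paired difference has variance 2(1 − 0.6) = 0.8 in raw SD units, so these are 0.09, 0.22 and 0.45 raw SD.

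**The plan's own figure.** For the within-between interaction, λ = f² × N × 2/(1 − ρ), on 1 and 118 df.

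- 0.24 read as f: λ = 0.0576 × 120 × 5 = 34.56, power 0.9999. Power of 0.95 would need only N = 48.
- 0.24 read as d (f = 0.12): λ = 0.0144 × 120 × 5 = 8.64, power 0.830. Power of 0.95 would need N = 184.
- Neither gives 120. For 120 to give exactly 0.95, λ must be 13.21 (f about 0.148).

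I carry all three baselines forward.

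**Model.** Let D = insulin minus placebo = τ_g + π·s + e, where s is +1 or −1 by order, π is the change from session 1 to session 2, and SD(e) = 1. Without a period term the error variance is 1 + π². Under simple randomisation the effective noncentrality is λ/(1 + π²). The balanced-order figures are from simulation (60,000 runs).

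| | π = 0.1 | π = 0.25 | π = 0.5 |
|---|---|---|---|
| Error variance, 1 + π² | 1.01 | 1.0625 | 1.25 |
| Equivalent N, 120/(1 + π²) | 118.8 | 112.9 | 96 |
| Power from 0.95, simple randomisation | 0.948 | 0.938 | 0.897 |
| Power from 0.83, simple randomisation | 0.827 | 0.807 | 0.741 |
| Power if 0.24 is f, simple randomisation | >0.999 | >0.999 | >0.999 |
| Power from 0.95, balanced order | 0.949 | 0.942 | 0.920 |
| Power from 0.83, balanced order | 0.828 | 0.814 | 0.765 |

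Simulation of the simple-randomisation case for the first two baselines (40,000 runs) agrees to within 0.003.

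**Type I error, overall.** Under simple randomisation it is about 5% at all three values. With balanced order it is 4.9%, 4.4% and 2.8%: the estimate does not shift, but the error term is too large, so the test is conservative.

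**Type I error, given the realised split** (100,000 runs, no period term). The smoker estimate shifts by π × (difference in order counts)/60. At 36:24 that is 0.02, 0.05 and 0.10 SD. If the numbers in a given order differ between the groups by k, the interaction shifts by π × 2k/60. At k = 10 that is 0.03, 0.08 and 0.17 SD.

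| Order split, smokers and non-smokers | π = 0.1 | π = 0.25 | π = 0.5 |
|---|---|---|---|
| 33:27 and 27:33 | 5.0% | 5.1% | 5.3% |
| 35:25 and 25:35 | 5.3% | 6.5% | 10.0% |
| 36:24 in both | 4.9% | 4.3% | 2.9% |
| Smokers alone, 36:24, paired t test | 5.1% | 5.8% | 7.9% |

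The last row is illustrative, because Section 12.0 names no test for smokers alone. Under simple randomisation (exact binomial), a smoker split of 36:24 or worse has probability 0.155. Order counts differ between groups by 6 or more with probability 0.315, and by 10 or more with probability 0.082.

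**With period in the model.** Type I error is 4.9% to 5.1% in every case, and power returns to about 0.95 or 0.83. For λ = 13.21, power on 118, 117 and 116 df is 0.95000, 0.94997 and 0.94995.

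**The case against.** The strongest reply is that little may be lost. Section 12.0 names a G*Power procedure in which 0.24 would naturally be Cohen's f. On that reading power stays above 0.999 at every session effect assumed here. The visible losses need either the d reading or a back-solved effect size, neither of which the documents state. The session effect itself is assumed, and at 0.1 or 0.25 SD the loss is at most about 2 percentage points. The power inputs also belong to ERN, not accuracy. Finally, random order makes the planned test valid overall. The 10.0% figure needs both the largest assumed effect and opposite imbalance in the two groups, and chance imbalance is already reflected in the standard error.

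All of this stands as a limit on size. The conditional error rates are secondary and do not show systematic bias. It does not answer the omission, however. The sponsor cannot know the session effect in advance, and adding the term after seeing the data would be an unplanned model choice. Balancing the order is not a substitute either: it removes the shift but leaves the error term inflated.

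**Conclusion.** The concern holds. The planned model omits period in a two-period crossover, and the consequence is mainly lost precision on the interaction for which the sample size is set. At an assumed session effect of 0.5 SD of the paired difference, simple randomisation of order leaves the precision of 96 of the 120 participants. Power then falls by about 5 points from a 0.95 baseline or 9 points from 0.83. At 0.25 SD the loss is 1 to 2 points, and at 0.1 SD it is negligible. There is no overall inflation of type I error. These sizes rest on the assumed session effect, on carrying the correlation and effect size given for ERN over to accuracy, and on 0.24 not being Cohen's f. The omission is certain and its importance is not. The change is worth making because it costs almost nothing.

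**What to change.** Add period to the model in Section 12.0. In the repeated-measures ANOVA, enter treatment order as a between-subject factor together with its interaction with treatment, which in a two-session crossover is the period effect. An equivalent mixed model would also do. Add period x group if learning may differ by smoking status. Report the insulin effect in smokers from the same model, since that is the Section 3.0 hypothesis. Unless Figure 1 or the unavailable sections already provide for it, allocate order in blocks separately within smokers and within non-smokers.

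The cost is one sentence of analysis text, a blocked list per smoking group if none exists, and one or two error degrees of freedom (117 or 116 instead of 118). No new data, visits or participants are needed.

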2.0 Background/Scientific Rationale

Describe the research problem and provide rationale for the research: Although there are several FDA-approved treatments for smoking cessation, only 6% of an estimated 40 million smokers successfully quit. Taking a more patient-specific approach to resolving this healthcare concern may lead to more efficacious outcomes. The purpose of finding a biomarker is to enhance future drug development of new smoking cessation pharmacotherapeutic agents. In addition to characterizing the biomarker, we will test whether intranasal insulin – an investigational drug – can improve go/no-go accuracy in smokers.

Briefly summarize prior experience and/or history relevant to the research: The rationale for using intranasal insulin is its efficacy in relieving cognitive deficits as reviewed in several papers (Shemesh et. al., 2012, de la Monte 2013, Ott et. al., 2012, Reger and Craft 2006, Strachan 2005, Fehm 2000).

It is hypothesized that intranasal insulin will relieve cognitive dysfunction in smokers as shown in previous studies (Franken et al., 2010; Luijten et al., 2011b).

Identify any investigational agents, drugs, devices, or biologics that will be administered or implanted into subjects: For this research study, smokers and non-smokers will be administered intranasal insulin (Novolin R, 60 IU) and placebo. Placebo will consist of sterile water with 14% NaCl. During administration of either intranasal insulin or placebo, participants will receive 1 spray in each nostril every 3 minutes for a total of 6 sprays. AeroPump delivers 0.1 ml of liquid per spray. Since the concentration of insulin in Novolin R is 100 IU/mL, six sprays will deliver the 60 IU dose.

Summarize relevant preclinical data: See “Briefly summarize prior experience and/or history relevant to the research” (above).

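### The only power statement is for ERN, not for the go/no-go accuracy that the trial analyses, and its 120 participants do not follow from its stated inputs

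*Combined protocol and SAP*

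**What the plan says.** **Outcome.** Section 3.0 sets the aim as to "evaluate go/no-go accuracy as a neurologic biomarker of smoking behavior" and adds: "Our hypothesis is that following intranasal insulin administration, smokers will have an improved go/no-go accuracy". Section 2.0 likewise says the trial will test whether intranasal insulin "can improve go/no-go accuracy in smokers". The analysis sentence of 12.0 reads "Go/no-go accuracy will be evaluated in a 2 x 2 repeated measure ANOVA", with group, treatment and their interaction as terms.

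**Sample size.** The sample-size paragraph of 12.0 takes its effect size from a cited study of error processing in smokers: "In that study, effect size was 0.24". It does not say which metric, outcome or contrast this figure describes. The calculation was done in G*Power "for an ANOVA test, repeated measures and within-between interaction", with two within and two between, "a base correlation=0.6; power=0.95; alpha=0.05, the total of 120 participants (60 per group"). This total "is required to capture an interaction between group and treatment on ERN". The same section describes the 120 as participants who complete the study.

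**ERN.** The abbreviation is not defined and occurs nowhere else in the plan. Section 6.1 refers once to event-related potential testing. No such endpoint or analysis is described.

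**The concern.** There are two separate problems.

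1. **The powered outcome is not the analysed outcome.** A power of 0.95 for an interaction on ERN says nothing about the interaction on accuracy, which has its own variability, between-session correlation and plausible effect. No input in 12.0 is identified as belonging to accuracy. Nor can a reader tell whether ERN is left over from another plan or is an intended outcome missing from 3.0 and from the analysis paragraph.
2. **The number does not appear to follow from its inputs.** An effect size of 0.24 with no metric can mean several things, and these lead to very different sample sizes.

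This is the trial's only sample-size justification. If the interaction on accuracy turns out null, nobody could say from the plan which size of effect the trial was able to exclude. If ERN is in fact an outcome, leaving it out of the objectives and the analysis leaves room to choose between outcomes after the data are seen.

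**Working it through.** **Inputs, all from 12.0:** effect size 0.24 (metric not stated); 2 groups; 2 repeated measures; correlation 0.6; alpha 0.05; power 0.95; stated total 120 (60 per group).

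**Formula.** For the within-between interaction with k = 2 groups and m = 2 measures, the F test has 1 and N − 2 degrees of freedom and noncentrality

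λ = f² × N × m / (1 − ρ) = f² × N × 2 / 0.4 = 5 f² N.

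In a 2 x 2 layout the difference-in-differences equals 4f, in units of the SD of a single measurement.

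**Attempt to reproduce 120**, with ρ = 0.6 and equal groups:

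| Reading of 0.24 | f | N for power 0.95 | Power at N = 120 |
|---|---|---|---|
| Cohen's f | 0.24 | 48 | 0.9999 |
| Cohen's d, with f = d/2 (difference-in-differences 0.48 SD) | 0.12 | 184 | 0.830 |
| Difference-in-differences of 0.24 SD, f = 0.24/4 | 0.06 | 724 | 0.308 |
| Correlation r | 0.247 | 46 | >0.999 |
| f squared | 0.490 | 14 | >0.999 |
| Partial eta squared | 0.562 | 12 | >0.999 |

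For f = 0.24, λ at N = 48 is 5 × 0.0576 × 48 = 13.82 and power is 0.953; N = 46 gives 0.945. For f = 0.12, λ at N = 184 is 5 × 0.0144 × 184 = 13.25 and power is 0.952; N = 182 gives 0.9496.

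G*Power's alternative effect-size options do not give 120 either: f = 0.24 gives 228 or 230. Working backwards at ρ = 0.6, 120 participants have power 0.95 only at f = 0.148.

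**Near misses.**
- f = 0.24 with the correlation at 0 gives 116 (power 0.958 at 120), but the plan states 0.6.
- f = 0.12 with four repeated measures and two groups gives 122 (power 0.949 at 120), but the design has two treatments in two sessions and a 2 x 2 ANOVA.
- Dropout does not close the gap. Going from 48 to 120 needs 60% loss (48/0.4 = 120), and the 120 are completers.

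**What 120 completers can detect.** Solving for f at N = 120 and multiplying by 4:

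| Correlation | 80% power | 95% power |
|---|---|---|
| 0.6 (the plan's value, stated for ERN) | f = 0.1153, 0.46 SD | f = 0.1484, 0.59 SD |
| 0.3 (assumed here for sensitivity) | f = 0.1525, 0.61 SD | f = 0.1963, 0.79 SD |

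A simulation of 20,000 runs with 60 per group, using a t-test on within-person differences, agreed. At ρ = 0.6, 0.461 SD gave power 0.798 and 0.594 SD gave 0.953. At ρ = 0.3, 0.61 SD gave 0.801 and 0.785 SD gave 0.949.

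**Within-smoker contrast.** The hypothesis in 3.0 is about smokers. For insulin versus placebo in 60 smokers, a paired test has λ = 60 d² / (2 × (1 − 0.6)) = 75 d². It detects 0.33 SD with 80% power and 0.42 SD with 95% power.

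**The case against.** **The number may have an origin.** The text of 12.0 speaks of two within and two between factors. If two within factors were entered as four repeated measures, and 0.24 was taken as Cohen's d, the result is 122, with alpha, power, correlation and 0.24 unchanged. This is the closest match that leaves those four values alone. It may explain where 120 came from, but it does not support it. It reads the within factors as four measures while still reading the between factors as two groups; reading both literally (four measures, four groups) gives 168. It also contradicts the two-session design, and the result would still be for ERN.

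**120 may be ample.** This stands as a possibility. If 0.24 is f and carries over to accuracy, 120 is 2.5 times the 48 required. Nothing here shows that the trial is too small.

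**ERN may be a real outcome.** Section 1.0 mentions non-invasive equipment for the biomarker. Section 6.1 schedules 20 minutes of equipment setup and describes a second visual task. The references include an equipment manual and a study of neural correlates of performance monitoring. These are consistent with electrophysiological recording, but none makes ERN an endpoint. If it is one, 3.0 and the analysis paragraph are incomplete.

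**The correlation of 0.6 is also not shown to be for accuracy.** This is correct. The detectable differences above hold only on that condition, so a value at 0.3 is given beside each and 0.6 should be labelled an assumption.

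**Conclusion.** Both parts hold, and the paragraph must be corrected. The outcome mismatch follows from the text alone. The failure to reproduce 120 holds for every reading tried that keeps the stated inputs and the two-group, two-treatment design; the list of readings is not exhaustive.

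The direction of the error is unknown. Power at 120 runs from 0.31 to above 0.999 depending on what 0.24 means, and that assumes the figure applies to accuracy at all. No required sample size for accuracy can be derived, since the documents identify no effect size, SD or correlation for it. What can be stated is the detectable difference, given 120 completers split equally, alpha 0.05 and an assumed correlation.

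**What to change.** Rewrite the sample-size paragraph of 12.0:

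1. Make go/no-go accuracy the outcome of the power statement. If ERN is an intended outcome, add it to 3.0 and to the analysis paragraph. Deleting the word ERN is not enough, because that would claim 0.95 power for accuracy from an effect of unknown outcome.
2. State the metric, outcome and contrast of 0.24 and rerun the calculation, or stop using 0.24 as the expected interaction.
3. Replace the 0.95 claim with wording such as: *With 120 completers (60 per group), alpha 0.05 and an assumed between-session correlation of 0.6, the group-by-treatment test on go/no-go accuracy has 80% power for a difference-in-differences of 0.46 SD and 95% power for 0.59 SD. If the correlation is 0.3 (assumed for sensitivity), these are 0.61 SD and 0.79 SD.*
4. Optionally, add the contrast hypothesised in 3.0: *Insulin versus placebo in 60 smokers has 80% power for 0.33 SD and 95% power for 0.42 SD at a correlation of 0.6.*
5. Give the SD of accuracy and its source, if there is one, so that these can be read in percentage points.

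The cost is one reworded paragraph, plus a line in 3.0 and one in the analysis paragraph if ERN is retained. No participants are added and the model is unchanged. The drawback is that the stated power may become less favourable. Detectable differences also describe what 120 can do rather than justify choosing 120, so a substantiated effect for accuracy would be better if one exists.
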